1 ETHICS/PROTECTION OF HUMAN SUBJECTS

1.1 Institutional Review Board (IRB)

This study will be conducted in compliance with current Good Clinical Practices (GCP) and Title 21 Part 56 of the United States of America Code of Federal Regulations (CFR) relating to IRBs.

1.2 Ethical Conduct of Study

The study will be conducted in accordance with GCP defined by the International Conference on Harmonisation (ICH) and the ethical principles of the Declaration of Helsinki.

1.3 Subject Information and Consent

This study will be conducted in compliance with Title 21 Part 50 of the United States of America Code of Federal Regulations (CFR), Federal Regulations, and ICH Guidance Documents pertaining to informed consent. At the first visit, prior to initiation of any study-related procedures, subjects will be informed about the nature and purpose of the study, participation/termination conditions, and risks and benefits. Subjects will be given adequate time to ask questions and become familiar with the study prior to providing consent to participate. Subjects will give their written consent to participate in the study and will be provided with a copy of the fully executed consent form for their records.

Some of the subjects in this study may be unable to provide informed consent due to cognitive impairment. The capacity to consent is gauged by an experienced licensed clinician investigator during the consent process through an evaluation of the participant's understanding of their condition, their options for treatment, their understanding of the potential benefits and risks of participating in the clinical trial and of their understanding regarding the voluntary nature of their participation in the trial. In addition, participants are evaluated for their level of orientation and understanding of what will happen during the trial. This process is recorded as part of the consent discussion documentation.

Subjects who are deemed unable to provide consent will be given the opportunity to assent, and consent will be obtained from a legally authorized representative. Subjects who are unable to assent or who object to participation in the study will not be enrolled.

2 INTRODUCTION: BACKGROUND INFORMATION AND SCIENTIFIC RATIONALE

2.1 Background Information

2.1.1 Alzheimer's Disease and Mild Cognitive Impairment

Alzheimer's disease (AD) is the most prevalent form of dementia affecting more than 5,000,000 people in the US and an estimated 20,000,000 people worldwide, according to the Alzheimer's Association¹. AD causes progressive neuronal degeneration, resulting in progressive memory loss, dementia and death. AD has no known cure or preventative as yet; however, treatments exist that can temporarily and modestly at best ameliorate dementia symptoms.

Mild cognitive impairment (MCI) is the term used when there is clinical concern about cognitive decline and evidence of impairment(s) in cognitive testing, more than expected for the patient's age and educational background, but not so severe that the person cannot manage their daily functioning without more than minimal assistance. MCI is frequently, though not always, a transitional, prodromal phase of dementia due to Alzheimer's disease. "Dementia" is present when independent daily functioning is affected.

AD is characterized by the presence of amyloid- β (A β) plaques, tau neurofibrillary tangles and loss of neurons and synapses in the cerebral cortex, particularly in association areas that subserve cognition. A β has been the target of many recent clinical trials; however, these studies have failed to find that reducing amyloid meaningfully slows progression of dementia. It is increasingly evident that AD is a complex disorder with multiple metabolic, inflammatory, vascular and other pathophysiological processes beyond amyloid and tau proteinopathies contributing to neurodegeneration. There is now increasing attention to intervening in these non-amyloid pathways to stem the tide of neurodegeneration in AD.

2.1.2 Alzheimer's Disease and the Immune Response

Inflammation and immune responses (IIR) have major roles in the pathophysiology of Alzheimer's disease (AD). IIR encompasses many complex and highly regulated biological processes with which immune local tissue cells respond to tissue injury and maintain organ function and organismal homeostasis. AD's pathognomonic amyloid- β (A β) peptide itself is hypothesized to be a dysregulated ancient innate immune response to allo- or auto-stimuli in the brain.² A β oligomers and aggregates in AD are thought to elicit or exacerbate IIR,³ promoting vicious cycles of protein misfolding, endoplasmic reticulum stress, deranged metabolic signaling and mitochondrial function, oxidative/nitrosative stress, and cell death. There is tremendous interest and rapidly growing academic, biotech and pharma research on IIR therapeutic approaches in AD and AD-related disorders as similar vicious cycles have been proposed for α -synuclein pathologies in LBDs,^{4,5} tau pathologies in FTD-tau and other tauopathies,^{6,7} and TDP-43 pathology in FTD-TDP and ALS.^{8,9}

Peripheral inflammatory markers may serve as biomarkers of AD disease state and distinguish healthy older adults from middle-aged adults, and healthy older adults from those with mild cognitive impairment (MCI) or Alzheimer's Disease¹⁰. Inflammatory biomarkers may even predict those who will convert from MCI to AD over a two-year period¹¹⁻¹³. Innate immune function is affected by progression of AD; Monocytes of subjects with MCI or AD induce a greater NLRP3 and NLRP1 inflammasome response to extrinsically applied amyloid beta than do healthy controls¹⁴. The adaptive immune system is also involved in AD progression: T-cell reactivity to amyloid beta increases with age as well as progression of AD¹⁰, and with worsening disease, clonal populations of CD4+ and CD8+ T-cells can be found in the cerebrospinal fluid^{15,16}. Regulatory T cells (Tregs) are of particular significance to AD. While augmenting Tregs increases the number and function of microglia associated with amyloid beta plaques, and improves cognitive functions^{12,17-19}, they are fewer in number over the course of disease²⁰.

There is tremendous and rapidly growing academic, biotech and pharma research on IIR therapeutic approaches in AD and AD-related disorders as similar vicious cycles have been proposed for α -synuclein pathologies in LBDs,^{5,21} tau pathologies in FTD-tau and other tauopathies,^{22,23} and TDP-43 pathology in FTD-TDP and ALS.^{24,25}

2.1.3 BCG Rationale

An Open Label Trial to Evaluate the Effects of BCG Immunization on Biomarkers of Inflammation/Immune Response and Alzheimer's Disease in Adults with Mild Cognitive Impairment and Mild-to-Moderate Dementia due to Alzheimer's Disease
Version Date#: October 13, 2022/Version 3.3

A potentially transformative IIR approach to AD prevention and disease modification that is safe, cheap and ready for testing now is Bacillus Calmette-Guérin (BCG) vaccination. Live BCG vaccination has been the mainstay of prevention of tuberculosis for almost 100 years, administered in billions of people in more than 180 countries, from infants to the elderly. Its only significant contraindication is immunocompromise. "Off-target" benefits of BCG vaccination were recognized early in its 40% reduction of all-cause mortality in children and its prevention of non-mycobacterial infections,^{26,27} and BCG is now being explored in clinical trials as a prophylaxis against COVID-19.²⁸ BCG has also demonstrated utility in treating non-infectious diseases. One major use is as a treatment for non-muscle-invasive bladder cancer, where high-dose intravesicular infusion is a treatment of choice,²⁹ and there has been interest in BCG's beneficial associations and effects in other cancers,³⁰⁻³² multiple sclerosis³³⁻³⁵ and type 1^{36,37} and type 2 diabetes.³⁸⁻⁴¹

In the CNS, 'sterile inflammation' resulting from autoimmunity, misfolded proteins, or cell damage or death can result in a neurotoxic environment if not adequately kept in balance. T-regulatory cells, or Tregs can regulate immunologic balance by controlling microglial and antigen presenting cell (APC) activation, inhibiting effector T (Teff) cells, and inducing astrocytic release of neurotrophins, thus effectively transforming a neurotoxic environment to a neurotrophic state. For example, two studies noted decreased neuronal cell death in a MPTP model of Parkinson's Disease, finding that the magnitude of dopaminergic preservation correlated with the magnitude of Treg response to BCG treatment.^{42,43} BCG's ability to induce and/or restore Treg immune balance is of great interest for treatment in AD,^{44,45} where preclinical models find that augmenting Tregs increases the number and function of microglia associated with plaques, and improves cognitive functions.^{18,46,47} In AD, Tregs may be overwhelmed due to their low numbers or dysfunction;⁴⁸ BCG may increase Treg number and function to rebalance the neurotoxic state to one of neuroprotection.⁵

Limited but provocative epidemiological analyses and *in silico* trial data support a benefit of BCG for AD. A large retrospective analysis found that older, non-demented adults treated with intravesicular BCG for bladder cancer had a significant 4-fold lower risk of subsequent AD over a median 8-year follow-up period than those treated with other means.⁴⁵

BCG, a highly safe, live, attenuated vaccine used throughout the world to prevent tuberculosis and confers many health-promoting non-specific effects, from preventing infectious disease to treating cancers. These effects rely on its induction of trained and heterologous immune responses in the host. Such immune effects directly overlap and influence immune responses known to occur in CNS disease; non-human studies have found benefit to BCG vaccination on models of Parkinson's and Alzheimer's diseases, including cognitive improvement. These studies provide the impetus for our initiating clinical trials with BCG oriented towards primary prevention of AD in older adults or disease modification and secondary or tertiary prevention in adults whom AD pathological changes are already in motion. This pilot study initiates this program, with focus on the immune consequences of treatment and potential changes in AD-specific biomarkers and cognition after vaccination. The BCG strain used in this study is not approved in the US for immunization against tuberculosis or for the treatment of AD.

A pilot, open-label study of BCG immunization (Protocol#2020P002042) in both healthy older adults and adults with Mild Cognitive Impairment is currently underway with a focus on the immune consequences of BCG vaccine and potential changes in AD-specific biomarkers and cognition after vaccination. The 3-month, open-label study has so far demonstrated that repeated administration of BCG vaccine is safe and tolerable in healthy adults and adults with mild cognitive impairment between the ages of 55 and 80 years old. Following two intradermal vaccinations to participants in the unblinded study, there have been no serious adverse events, no clinically significant abnormalities detected in safety lab (eg. metabolic, hematologic, and immune labs) or vital sign measurements, and only mild-to-moderate, expected adverse events related to the lumbar puncture and blood draw procedures in the protocol. This small-scale study has informed the trial design and validated the assays included in the proposed in this protocol.

3 STUDY DESIGN

3.1 Overall Study Design and Plan

This single-site, open-label trial will investigate the effects of BCG vaccination on IIR and AD biofluid biomarkers, magnetic resonance imaging (MRI) biomarkers, and neurocognitive/behavioral functioning over a one-year period in older adults with mild cognitive impairment (MCI) to mild-to-moderate dementia due to AD. This study will also gather data on tolerability and safety. Safety will continue to be followed in the second year by phone.

Up to twenty five participants meeting eligibility criteria will be enrolled. Each participant will receive two intradermal BCG vaccinations spaced 4-6 weeks apart and will be evaluated 12, 26, and 52 weeks after the initial immunization. Cerebrospinal fluid (CSF), blood, MRI (in a subset of patients), and neurocognitive/behavioral assessments will be collected at Screening (CSF, blood, and cognitive/behavioral), Week 1 (MRI and cognitive/behavioral), Week 4 (blood), Week 12 (CSF, blood, and cognitive/behavioral), Week 26 (Blood and cognitive/behavioral) and Week 52 (all) to assess biomarkers and safety. Safety measures, including updated medical history and adverse events, will be collected at Week 78 and Week 104.

3.2 Study Objectives

The primary objectives of this study are:

1. To assess the safety and tolerability of BCG vaccination in older adults with MCI and mild to moderate dementia due to AD.
2. To investigate the potential of BCG vaccination as an immunomodulatory and CNS-protective agent for AD by evaluating changes from baseline in IIR and AD biomarkers in blood and CSF following BCG vaccination;
3. To measure changes in neurocognitive/behavioral functioning following BCG vaccination (MoCA, RBANS, CDR-SB, NPI-Q, HADS, FAQ, DCT Clock).

The secondary objective of the study is:

1. To measure changes in structural and functional neuroimaging following BCG vaccination;

3.3 Study Outcome Measures

3.3.1 Safety Measure Outcomes

Medical history, adverse events, and classic metabolic, hematologic, coagulation, and immune blood labs will be collected at Screening to determine eligibility. Adverse events will be solicited at every visit. Hematologic and coagulation blood labs will be repeated at Week 12 and Week 52 visits for LP safety. Vital signs will be measured at all in-person visits. Additionally, four weeks after the first injection, we will assess the injection site and evaluate for any signs of systemic infection prior to second BCG vaccination in the other arm. Vaccination sites will also be assessed at Weeks 12, 26, and 52. We will use the FDA Toxicity Grading Scale, as performed in vaccine trials, to denote changes from baseline. Safety measures, including updated medical history and adverse events, will also be collected at Week 78 and Week 104.

3.3.2 CSF and Blood Biomarker Outcomes

CSF and blood will be collected at Screening, Week 4 (blood only), Week 12, Week 26 (blood only), and Week 52 visits to examine biochemical biomarkers of:

1. Target engagement: BCG, purified protein derivative (PPD) and / or mycobacterium tuberculosis (heat-killed, mTB) – induced cytokine response in peripheral blood cells will be used to evaluate for BCG vaccine-induced immunity.
2. Pharmacodynamic response: a) Circulating cytokines and other related blood- and CSF-based IIR biomarkers relating to innate and adaptive immune responses; b) Epigenetic changes in peripheral blood cells and / or CSF- derived cell populations as indicators that BCG can lead to long term changes in peripheral and central nervous system immune cells.
3. AD pathophysiology: Amyloid- β 42/40, phospho-tau, total tau and / or neurofilament light protein biomarkers (ATN) and other exploratory AD-relevant synaptic and IIR biomarkers may be compared within subjects over time and between subjects and groups.
4. BCG effects on the interactions of IIR and amyloid: We will perform PBMC stimulation with A β 42 and positive-control antigens (e.g. lipopolysaccharide) and measure the molecular response in the supernatant at multiple timepoints after BCG /treatment. A β 42 has immunostimulatory / inflammatory effects that increase with AD progression and may be modulated by an immune-provoking stimulus such as BCG.
5. Additional related Alzheimer's Disease and immune measures in plasma, CSF, and their cell populations at the transcriptional, protein, or epigenetic levels.

We have several robust platforms in the [name] lab (which serves as the Biomarker Core of the Massachusetts Alzheimer's Disease Research Center) to conduct these assays, including highly validated Euroimmun assays, Fujirebio Lumipulse assays, Meso Scale Discovery with plates run on a new Tecan EV0200 multi-functional robotic liquid handling platform, and Quanterix SR-X for ultrasensitive Simoa assays. We have exhaustively validated many assays specifically for use in short-term clinical trials⁴⁹, and all assays that we propose demonstrate good precision and biotemporal stability. Change in a composite score from Baseline will be used as an outcome of response to BCG.

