6 STUDY PROCEDURES

6.1 Schedule of Events

Activity	Phone Screen	Visit 1 Screen Visit		Visit 2 Baseline Visit	Visit 3	Visit 4	Visit 5	Phone Check 1	Visit 6/ET	Phone Check 2	Phone Check 3
		Day \geq -45		Week 1	Week 4	Week 12	Week 26	Week 39	Week 52	Week 78	Week 104
		SVa	SVb	Day 1	Day 28 + 14	Day 84 \pm 5	Day 182 \pm 14	Day 273 \pm 5	Day 364 \pm 28	Day 546 \pm 28	Day 728 \pm 28
Informed Consent		X									
Inclusion/Exclusion Review	X	X		X							
Demographics	X	X									
Medical History Review	X	X	X	X	X	X	X	X	X	X	X
Concomitant Medication Review	X	X	X	X	X	X	X	X	X	X	X
Family History Review		X									
Vital Signs, Height, and Weight ¹		X	X	X	X	X	X		X		
Physical & Neurological Exam ²		X									
Fundoscopy						X			X		
Screening Labs ³		X									
BCG Vaccination				X	X						
Injection Site Monitoring ⁴					X	X	X		X		
LP Safety Labs ⁵		X				X			X		
Blood Draw for Biomarkers			X	X	X	X	X		X		
CSF Draw for Eligibility & Biomarkers			X			X			X		
Optional MRI ⁶				X					X		
RBANS, NPI-Q, HADS				X		X	X		X		
MoCA, FAQ		X				X	X		X		
CDR				X					X		
DCT Clock				X			X		X		
Adverse Event Review		X	X	X	X	X	X	X	X	X	X

[1] Height measured at screening only. Weight measured at screening, week 26, and week 52

[2] Physical and neurological examinations will be performed at screening and at any other time if indicated per clinician investigator judgement

[3] Eligibility lab tests include CBC w/ diff, CMP, TSH, Folate, B12, HIV antibodies, serum immunoglobulins, ESR, CRP, QuantiFERON-TB Gold Test/T-spot TB test, urinalysis, PT/INR

[4] Vaccination site monitoring may include photographs of the injection site if indicated per clinician investigator judgement

[5] LP safety labs include PT/INR and CBC w/ diff

[6] Multi-sequence MRI for structural and functional measures include T1 MP-RAGE, T2 FLAIR, DWI, DTI, BOLD, ASL

An Open Label Trial to Evaluate the Effects of BCG Immunization on Biomarkers of Inflammation/Immune Response and Alzheimer's Disease in Adults with Mild Cognitive Impairment and Mild-to-Moderate Dementia due to Alzheimer's Disease

Version Date#: October 13, 2022/Version 3.3

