6.2.1.2 Screening Visits (Visit 1; Day ≥-45)

All subjects who are eligible after a telephone pre-screening will be invited to MGH CNY for Screening that will include 2 separate visits.

The first visit (SVa) will take approximately 2 hours and following procedures will be performed:

- Obtain written informed consent from subject
- Review inclusion and exclusion criteria
- Obtain medical and family history including COVID-19 history, concomitant medications and therapies
- Vital signs, height, and weight
- Obtain demographic information
- Neurocognitive and behavioral assessments: MoCA (version 8.1), CDR, FAQ
- Perform a physical, including inspection for BCG scar on either deltoid
- Perform a neurological examination
- Blood draw for screening labs

- CBC with differential
- Comprehensive metabolic panel (CMP)
- Thyroid stimulating hormone (TSH)
- B12
- Folate
- HIV antibodies
- Tuberculosis (QuantiFERON-TB Gold Test/T-Spot TB Test)
- C-Reactive Protein (CRP)
- Erythrocyte sedimentation rate (ESR)
- Serum immunoglobins (IgA, IgG, IgM)
- PT/INR
- Urinalysis
- Assess and document adverse events (AEs) after subject signs ICF

If the participant is still eligible after the first Screening visit (SVa), they will be invited to come back for a second Screening visit (SVb) which will take approximately 1 hour. The following procedures will be performed:

- Vital signs
- Blood draw for biomarkers
- Fasting CSF draw for screening (if required) and baseline biomarkers
- Assess for changes to medical history, concomitant medications and/or adverse events

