6.2.2 Baseline Visit/Visit 2 (Day 1)

All subjects who pass screening will return to MGH CNY for the Baseline visit. At this visit, baseline clinical measures will be collected, and the first BCG injection will be administered. The Baseline visit will occur within 45 days of the screening visit. Baseline measures may be collected up to 3 days before the first BCG dose is administered. The date of the first BCG injection will be considered “Day 1”. The visit will take approximately 3-4 hours and will include:

- Vital signs
- Review inclusion and exclusion criteria
- Assess for changes to medical history, concomitant medications and/or adverse events
- Neurocognitive and behavioral assessments: RBANS (form a), NPI-Q, HADS, DCT Clock
- Blood draw for biomarkers
- MRI (optional)
- First BCG administration followed by 30 minutes of monitoring

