8.3 Biofluid Biomarker, Clinical and Neuroimaging Endpoints

The change in the following assessments from Screening and/or Baseline to each post-baseline visit as described below based on the Schedule of Activities after BCG vaccination:

- Biochemical Biomarkers in Blood (Screening/Baseline, Weeks 4, 12, 26, 52) and CSF (Screening/Baseline, Weeks 12, 52) : a) Target engagement (e.g., PPD-induced PBMC cytokine release); b) Pharmacodynamic response (e.g., circulating cytokines in blood and CSF); c) AD pathophysiology (e.g., amyloid-b, tau and neurofilament light in CSF and blood); d) PBMC stimulation with AD-relevant immunogens (e.g., amyloid-b); e) Other novel biochemical biomarkers
- Clinical Neurocognitive and Behavioral Measures (Baseline, Week 12, 26 and 52): MoCA, RBANS, CDR-SB, NPI-Q, HADS, DCT Clock and FAQ
- Multi-Sequence Structural and Functional MRI (Baseline, Week 52)

Mixed-effects Model for Repeated Measures models will be used for biofluid and clinical endpoints to calculate differences at each post-baseline visit in which the biomarker is collected using baseline assessment as a covariate. Observed Case analysis will be used for differences in change of MRI measures over 52 weeks.

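### Biomarker blood is drawn before dose 1 at both SVb and Day 1, but sections 3.1 and 3.3.2 omit the Day 1 draw and section 8.3 does not say which value is the blood baseline

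*Combined protocol and SAP*

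**What the plan says.** Four places schedule two pre-dose draws:

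- Section 6.2.1.2 puts biomarker blood at SVb, in the same visit as the "Fasting CSF draw for screening (if required) and baseline biomarkers".
- Section 6.2.2 lists "Blood draw for biomarkers" at the Baseline visit, ahead of the first BCG administration, and adds: "Baseline measures may be collected up to 3 days before the first BCG dose is administered". On spacing it says: "The Baseline visit will occur within 45 days of the screening visit".
- In the Schedule of Events (6.1), the row "Blood Draw for Biomarkers" is marked at SVb, at Visit 2 (Day 1, also labelled Week 1) and at Visits 3 to 6.
- Table 2 (section 6.3.3) budgets 75 mL at SVb and 50 mL at Week 1.

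Two places list only one:

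- Section 3.1 reads "Week 1 (MRI and cognitive/behavioral), Week 4 (blood", so Week 1 carries no blood.
- Section 3.3.2 reads "CSF and blood will be collected at Screening, Week 4 (blood only), Week 12, Week 26 (blood only), and Week 52 visits", which passes from Screening to Week 4. The same section then makes change in a composite score from Baseline an outcome.

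Section 8.3 leaves the matter open. Its endpoint is "The change in the following assessments from Screening and/or Baseline to each post-baseline visit". For blood biomarkers it joins Screening and Baseline with a slash, and the repeated-measures model takes a single baseline assessment as covariate. No section says whether the blood baseline is SVb, Day 1, the last pre-dose value or a mean.

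**The concern.** Change from baseline in blood and CSF biomarkers is a primary objective (section 3.2), and section 8.1 names target engagement, measured on blood cells, alongside safety. Every participant is vaccinated and there is no concurrent control, so the pre-dose value is what each post-dose value is judged against.

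Two things follow from an undefined baseline. One of the two samples may go unused, which wastes precision in a trial expecting 12 completers (section 4.2). Or the analyst may settle between SVb, Day 1 and a combination separately for each marker. With many markers and open-label data, that choice could be made after the results are visible.

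**Working it through.** **1. Is the Day 1 draw really planned?** Table 2's totals answer this.

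- Biomarker volume: 75 + 50 + 75 + 125 + 125 + 125 = 575 mL, as stated.
- Routine tests: 3 + 9 + 9 + 6 = 27 mL, as stated. Overall: 575 + 27 = 602 mL, as stated.
- Without the Week 1 row the totals would be 525 and 552 mL.

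The stated totals need the 50 mL draw, so sections 3.1 and 3.3.2 are the ones out of line.

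**2. What would averaging gain?** The documents give no SDs or correlations for these markers, so the following are assumptions. Let each value have variance s², let p be the correlation between the two pre-dose draws, and let r be the correlation between either pre-dose draw and follow-up.

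- Variance of change, single baseline: 2s²(1 - r).
- Variance of change, mean of two: s²[(1 + p)/2 + 1 - 2r].

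If p = r, the ratio is 1.5(1 - r) / 2(1 - r) = 0.75 for any r: a 25% cut in variance, or 13.4% in standard error (square root of 0.75 = 0.866). A simulation at p = r = 0.7 gave 0.601 and 0.451, against 0.60 and 0.45 from the formulas.

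If the pre-dose draws are more alike (r = 0.7 throughout):

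| p | mean of two / single | cut |
|---|---|---|
| 0.80 | 0.50 / 0.60 = 0.833 | 17% |
| 0.90 | 0.55 / 0.60 = 0.917 | 8% |
| 0.95 | 0.575 / 0.60 = 0.958 | 4% |

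**3. With baseline as a covariate (p = r).** Residual variance is s²(1 - r²) with one draw and s²[1 - 2r²/(1 + r)] with the mean.

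| r | single | mean of two | cut |
|---|---|---|---|
| 0.3 | 0.910 | 0.862 | 5% |
| 0.5 | 0.750 | 0.667 | 11% |
| 0.7 | 0.510 | 0.424 | 17% |
| 0.9 | 0.190 | 0.147 | 22% |

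**4. In terms of this trial.** At p = r = 0.7, the 95% confidence half-width for a mean change falls from 0.49 to 0.43 SD with 12 participants, and from 0.43 to 0.37 SD with 15. Twelve participants with an averaged baseline match 12/0.75 = 16 with a single one in the equal-correlation case, but only 12/0.958 = 12.5 at the low end of step 2.

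**5. Target engagement.** Participants must have no prior BCG exposure and a negative tuberculosis test (section 4.1.1), so pre-dose mycobacterial responses may be low and less variable than post-dose ones. Suppose the pre-dose within-person variance is one quarter of that at follow-up (an assumption). The variance of change then goes from 1.25 to 1.125 units, a 10% cut, if true changes are equal. It goes from 2.25 to 2.125, a 5.6% cut, if true changes vary by one unit.

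**6. Comparability of the draws.** With independent errors, the mean beats the better single draw when (a² + b²)/4 < a², that is, when the larger error SD b is less than 1.73 times the smaller one, a.

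**The case against.** The strongest objection is that the two draws may not be duplicates. 75 + 50 = 125 mL is exactly the single-visit biomarker volume at Weeks 12, 26 and 52, so the baseline panel may be divided between the visits. Screening/Baseline in section 8.3 would then describe one baseline in two parts, and an assay run on only one draw has nothing to average. The documents do not settle this. Week 4 uses 75 mL on its own, so a smaller panel is possible, and section 6.3.3 describes the same general processing into plasma and blood cells without distinguishing visits. It is reasonable to expect that plasma markers, at least, can be measured on both. The limit stands for the other assays.

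Section 8.3 also refers to the visit schedule, which includes Day 1, and its loose wording covers a mixed list: MoCA and FAQ are taken at screening, RBANS, NPI-Q and HADS at Day 1, and CSF at SVb. A reader might infer that the wording was meant to allow a free choice of baseline. The documents do not support that. What remains is that the blood entry itself has no rule.

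Three further points stand. The lumbar puncture at SVb is fasting and no fast is stated for Day 1. Participants who roll over after placebo have no blood taken at their new Day 1 (section 6.1.1). And fixing the last pre-dose value as baseline would remove selection just as well as averaging; averaging is preferred only for its precision.

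**Conclusion.** The inconsistency and the undefined blood baseline are confirmed by the text and by Table 2's totals. Averaging is the better definition wherever both draws are assayed. It reduced variance in every scenario tried, by 4-25% for change from baseline and 5-22% for baseline-adjusted residuals.

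A reader might infer that every blood outcome, target engagement included, gains the full 25%. The documents do not support that. The figure needs the same assay on both draws, equal variances, and pre-dose draws no more alike than pre-dose and follow-up. The last is doubtful when the pre-dose draws are at most about 45 days apart and follow-up runs to Week 52.

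The sample size is set by feasibility with no power claim (section 8.1), so no stated operating characteristic is wrong. This is a definition that should be fixed before analysis, with a modest gain in precision attached.

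**What to change.** - In sections 3.1 and 3.3.2, add the Week 1 (Day 1) biomarker blood draw.
- In section 8.3, define the baseline for each blood biomarker assayed on both draws (plasma markers at least) as the mean of the SVb and Day 1 pre-dose values, on the log scale for cytokines.
- For each assay run on only one of the two draws, name that draw as baseline. The CSF baseline stays SVb.
- State that placebo-first roll-over participants use their original SVb and Day 1 draws. Both precede any BCG, though by about a month or more. This assumes that the randomised trial took blood at the same visits; its schedule is not reproduced here.
- Record fasting status at each draw.

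The text change is a few sentences and no blood is added to Table 2. The cost is extra assays on samples already drawn: possibly small for plasma markers, more for cell stimulation or epigenetic work. Any assay split across the two draws gets a clear baseline but no precision gain.
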